6.3.2.4 Definition of Maximum Tolerated Dose (MTD)

MTD is defined as the highest Ad5-*yCD/mutTK_{SR39}rep-hIL12* dose at which < 33% (< 1 of 3 or < 2 of 6) of any cohort develops DLT.

If 1 of 3 subjects in a cohort develops DLT, the cohort will be expanded to 6 subjects. If \geq 2 subjects out of 6 in a cohort develop DLT, MTD will have been exceeded at that dose. If there is a lower dose and if the cohort at that dose has not already been expanded to 6, the cohort will be expanded to 6 at the lower dose. If \geq 2 subjects develop DLT, MTD will have been

exceeded and the trial will stop.

6.3.3 Adverse Event Reporting Guidelines

Guidelines for adverse event reporting are depicted in **Table 9**. Adverse events that require reporting will be reported using the Adverse Event Reporting CRF specifically designed for this study.

Table 9. Adverse Event Reporting Requirements		
Not Serious	Serious AND unrelated to the agent/intervention	Serious AND possibly, probably or definitely related to the agent/intervention
Reporting is NOT required.	Reporting is NOT required	Report by phone/FAX/email to IRB within 24 hours of discovery of event. Written report to IRB, IBC, OBA and FDA within 10 calendar days. This includes deaths within 30 days of adenovirus injection.

6.4 Subject Removal and Study Stopping Rules

6.4.1 Subject Removal Rules

Every attempt will be made to obtain follow-up on subjects who have received the study medication.

- 6.4.1.1** The subject may withdraw from the study upon request of the participating subject or person with the power of attorney.
- 6.4.1.2** Noncompliance.
- 6.4.1.3** Intercurrent medical or psychiatric problem or institution of a concomitant medication that interferes with compliance with the protocol or places the subject at increased risk.
- 6.4.1.4** Dose-limiting toxicity (DLT).
- 6.4.1.5** Investigator's discretion, to the extent that subsequent clinical study requirements place the subject at unacceptable risks.

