5.1.3.7 Toxicity

The most common side effects associated with 5-FC (Ancobon[®]) + vGCV (Valcyte[®]) prodrug therapy include neutropenia and thrombocytopenia. In five previous phase 1/2 trials representing 79 subjects (36-44), 19 of 79 (24%) subjects exhibited grade 1 - 3 neutropenia and 26 of 79 (33%) subjects exhibited grade 1/2 thrombocytopenia. The prodrugs may also contribute to anemia (32 of 79 subjects or 41%) and possibly lymphopenia (69 of 79 subjects or 87%). Except for lymphopenia, the vast majority of these events are mild (grade 1) to moderate (grade 2). Sixty-four percent (64%) of the events of lymphopenia were moderate (grade 2) and 25% were severe (grade 3). All hematologic events are transient and self-limiting, and typically resolve within two (anemia, neutropenia, thrombocytopenia) to six (lymphopenia) weeks.

Other possible side effects associated with 5-FC (Ancobon[®]) + vGCV (Valcyte[®]) prodrug therapy include nausea, vomiting, diarrhea and headache.

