5.1.3.8.1 Cytopenia

5.1.3.8.1.1 Absolute neutrophil count < 1,000/ μ L or platelet count < 100,000/ μ L- reduce 5-FC and vGCV doses to 75%.

5.1.3.8.1.2 Absolute neutrophil count < 500/ μ L or platelet count < 50,000/ μ L- discontinue 5-FC and vGCV, and resume the drugs at 50% of the original dose when the neutrophil count is > 500/ μ L and platelets > 50,000/ μ L.

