6.3. Toxicity Assessments

6.3.1 Adverse Event Grading Criteria

Adverse events will be graded according to NCI's Common Terminology Criteria for Adverse Events (CTCAE) v4.03 (68). Adverse events will be documented using CRFs specifically designed for this trial.

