6.3.2.3 Definition of Dose-Limiting Toxicity (DLT)

Dose-limiting toxicity is defined as any of the following adverse events considered possibly/probably/definitely related to the study treatment.

6.3.2.3.1 \geq Grade 2 allergic reaction or generalized urticaria.

6.3.2.3.2 \geq Grade 2 cardiovascular or neurologic toxicity.

6.3.2.3.3 \geq Grade 3 hematologic or non-hematologic toxicity of any duration except for:

6.3.2.3.3.1 Grade 3 lymphopenia with recovery within 2 weeks.

6.3.2.3.3.2 Grade 3 anemia, leukopenia, or neutropenia that is reversible within 72 hours.

6.3.2.3.3.3 Grade 3/4 fever or flu-like symptoms that are reversible within 72 hours.

6.3.2.3.3.4 Grade 3 SGOT/SGPT that is reversible within 72 hours.

6.3.2.3.3.5 Grade 3 hyperglycemia that can be explained by patient's baseline comorbidity (i.e., diabetes).

6.3.2.3.3.6 Grade 3 hypermagnesemia that is reversible within 72 hours.

6.3.2.3.3.7 Grade 3 hypophosphatemia that is reversible within 72 hours.

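### After severe related cytopenia, the removal rule (6.4.1.4) and the prodrug restart rule (5.1.3.8.1.2) give opposite instructions for the same man, on the usual CTCAE reading of the counts

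*Combined protocol and SAP*

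**What the plan says.** Four parts of the protocol bear on this.

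- **Removal.** Item 6.4.1.4 of the Subject Removal Rules reads, in full, "Dose-limiting toxicity (DLT"). No exception or cross-reference is attached, and removal is not defined. The same section opens with "Every attempt will be made to obtain follow-up on subjects who have received the study medication".
- **Restart.** For neutrophils below 500/µL or platelets below 50,000/µL, 5.1.3.8.1.2 instructs staff to "discontinue 5-FC and vGCV, and resume the drugs at 50% of the original dose when the neutrophil count is" above 500/µL and platelets are above 50,000/µL. It mentions neither DLT nor removal.
- **DLT definition.** Section 6.3.2.3 covers events "considered possibly/probably/definitely related to the study treatment". Item 6.3.2.3.3 takes in everything at or above "Grade 3 hematologic or non-hematologic toxicity of any duration except for" a short list. The only entry for neutropenia is "Grade 3 anemia, leukopenia, or neutropenia that is reversible within 72 hours". Thrombocytopenia is not on the list.
- **Grading and attribution.** Section 6.3.1 adopts "Common Terminology Criteria for Adverse Events (CTCAE) v4.03" without printing its count cut-offs. Section 5.1.3.7 says that the most common side effects of "prodrug therapy include neutropenia and thrombocytopenia".

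**The concern.** The restart rule appears to apply almost only to men whom the removal rule has already taken off. The adenovirus is given once (5.1.2.9), so after day 1 the prodrugs are the only study therapy left to stop. If removal means anything for treatment, it means no more prodrug, and 5.1.3.8.1.2 says the reverse. Two members of staff, each following a valid section, would manage the same man differently just after a severe hematologic toxicity. That bears on his safety. It also bears on how later toxicity is described in a trial whose primary endpoint is toxicity through day 30.

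**Working it through.** The plan gives no figure to reproduce, and 8.2 says that a power calculation is not relevant. The check is a comparison of rules, followed by a bound on frequency.

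**1. Assumption on grades.** The cut-offs are not in the documents. I assume that in CTCAE v4.03 neutrophils below 500/µL are Grade 4 and 500 to below 1,000/µL Grade 3, and that platelets of 25,000 to below 50,000/µL are Grade 3 and lower counts Grade 4.

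**2. Each restart trigger against 6.3.2.3.3, for an event at least possibly related.**

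- Neutrophils below 500/µL: Grade 4. The 72-hour exception covers Grade 3 only, so this is a DLT whatever its duration.
- Platelets below 50,000/µL: Grade 3 or higher. No exception exists, so this is a DLT whatever its duration.

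**3. Check by enumeration.** Take neutrophils from 0 to 3,000/µL in steps of 50 and platelets from 0 to 300,000/µL in steps of 5,000, which gives 61 values of each.

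- Cells that trigger stop-and-restart: 61 × 61 − 51 × 51 = 3,721 − 2,601 = 1,120. All 1,120 are DLTs regardless of duration.
- Cells in the milder tier, 5.1.3.8.1.1 (reduction to 75%): 51 × 51 − 41 × 41 = 2,601 − 1,681 = 920. None is a DLT regardless of duration. Neutrophils of 500 to below 1,000/µL become one only if not reversed within 72 hours. That tier contains no restart, so the point is confined to 5.1.3.8.1.2.

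**4. Range if the assumptions are wrong.**

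| Change | Effect on the conflict |
|---|---|
| Neutrophils < 500/µL only Grade 3 | Neutrophil conflict limited to cases not reversed within 72 hours |
| Platelets < 50,000/µL below Grade 3 | Platelet conflict vanishes |
| Cytopenia judged unrelated or unlikely related | No DLT, so no conflict |

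**5. Frequency.** Section 5.1.3.7 reports 79 earlier subjects, with neutropenia of Grades 1 to 3 and thrombocytopenia of Grades 1 and 2. This implies 0/79 with Grade 4 neutropenia and 0/79 with thrombocytopenia of Grade 3 or more.

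- One-sided 95% upper limit for 0/79: 1 − 0.05^(1/79) = 0.037, or 3.7%.
- At that limit: 15 × 0.0372 = 0.56 men and 30 × 0.0372 = 1.12 men. These are upper bounds, not expected numbers.
- The earlier vectors lacked IL-12 (5.1.2.8), and the same section thinks it possible or likely that IL-12 will worsen both cytopenias. The bound may therefore be too low for this trial.

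**6. Treatment at stake.** The course is 7 days (5.1.3.4). Section 5.1.3.8.2 caps prodrug at 7 days in total whatever the dose, and bars a restart after more than 2 weeks of continuous suspension. A man who has taken d days has at most 7 − d left, so at most 6 once he has started.

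**The case against.** The strongest reply is that the conflict rests on a grading table that the documents do not reproduce and on attribution. This stands as a condition, and the range above shows what each part is worth. It does not remove the point. The protocol adopts the grading scale by name and names these two cytopenias as the commonest prodrug effects, so an attribution of at least possible is the expected case.

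A second reply is that the stakes are small: no such event is implied in 79 men, and at most the remainder of one week of prodrug is involved. That also stands. The limits on total days and on suspension sit in the creatinine section but are worded generally. Neither says whether a DLT bars a restart.

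A reader might infer two stronger things, and the documents support neither.

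- **That men with DLTs would drop out of the PSA, PSADT, failure and quality-of-life data, chiefly at the higher doses.** Section 6.4.1 opens by committing to seek follow-up on everyone treated, 6.6.4 follows all subjects for survival, and Table 10 has separate forms for discontinuing therapy and for long-term follow-up. The planned prodrug dose is the same in every cohort, and a dose gradient through IL-12 would be conjecture. What remains is that removal is undefined.
- **That the conflict distorts dose escalation.** Sections 5.1.2.5 and 6.3.2.4 count subjects who develop a DLT, and nothing takes a removed man out of that count. Under the stated assumption he is already a DLT when the question of restart arises.

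**Conclusion.** The contradiction is real and no section resolves it. For cytopenia at least possibly related to treatment, and with the assumed CTCAE v4.03 cut-offs, every trigger of 5.1.3.8.1.2 is also a removal event under 6.4.1.4. The two sections then point in opposite directions on further prodrug, whether removal means leaving treatment or leaving the study. With other cut-offs the conflict narrows as tabulated, and for cytopenia judged unrelated or unlikely related there is none.

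Its size is modest: a probably infrequent event and a few days of prodrug, with no effect on the DLT count, the MTD rule or any sample-size figure. It merits correction because it leaves the handling of a man with severe toxicity to whichever section is consulted.

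**What to change.** The sponsor should reconcile 5.1.3.8.1.2, 6.3.2.3 and 6.4.1.4 so that a single instruction governs prodrugs after a hematologic DLT, and should cross-refer to it from both the cytopenia section and the removal section. Which instruction is right is a clinical decision for the sponsor, and this review does not propose one.

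As a minor clarification, 6.4.1 should say that removal for DLT does not end scheduled follow-up, which agrees with its own opening sentence.

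The cost is about two sentences in a protocol amendment. No visits or assessments are added, because the follow-up schedule in Table 7 already exists.

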6.4.2 Study Stopping Rules

- 6.4.2.1** DLT in the first dose cohort.
- 6.4.2.2** If > 33% of enrolled subjects develop \geq grade 3 hematuria or urinary retention, the study will be stopped and the injection procedure re-evaluated.
- 6.4.2.3** Transmission of the Ad5-yCD/mutTK_{SR39}rep-hIL12 adenovirus to any subject contacts, including health care personnel.
- 6.4.2.4** Lack of availability of the Ad5-yCD/mutTK_{SR39}rep-hIL12

adenovirus.

6.4.2.5 Insufficient accrual.

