3.0 SUBJECT SELECTION

3.1 Number of Subjects

Fifteen to 30 men with locally recurrent prostate cancer after definitive radiotherapy.

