5.1.2.5 Ad5-yCD/mutTK_{SR39}rep-hIL12 Adenovirus Dose

The treatment schema is depicted in **Figure 5**.

Dosing of the Ad5-yCD/mutTK_{SR39}rep-hIL12 adenovirus is shown in **Table 5**. The starting dose level will be 1×10^{10} vp. The interval between dosing of the first two subjects in the first cohort should be ≥ 2 weeks.

All subjects in each cohort will be evaluated for ≥ 30 days before proceeding to the next cohort. If one of three subjects experiences a dose-limiting toxicity (DLT) (defined in Section **6.3.2.3**), three additional subjects will be enrolled at that dose level. If only one of six subjects experiences a DLT at a given dose level, the dose will escalate to the next cohort of three subjects. If two subjects experience a DLT at a given dose level, the maximum tolerated dose (MTD) is exceeded. Three

additional subjects will be enrolled at the previous dose level if there were only three subjects at that dose. The adenovirus dose will be escalated to a maximum of 1×10^{12} vp.

Table 5. Ad5-yCD/mutTK_{SR39}rep-hIL12 Dosing		
Cohort	# Subjects	Adenovirus Dose (vp)
1	3 to 6	1×10^{10}
2	3 to 6	3×10^{10}
3	3 to 6	1×10^{11}
4	3 to 6	3×10^{11}
5	3 to 6	1×10^{12}

Toxicity Assessments

[figure not shown]

Figure 5. Treatment Schema. Subjects will undergo a series of pre-treatment evaluations and must meet all of the eligibility criteria to be enrolled in the study. Subjects will receive a single intraprostatic injection of the Ad5-yCD/mutTK_{SR39}rep-hIL12 adenovirus at one of five dose levels (see Table 5) on day 1. Two days later (day 3), subjects will receive a one week (7 day) course of 5-FC (150 mg/kg/day) + vGCV (1,800 mg/day) prodrug therapy. Toxicity assessments will occur twice a week during the first two weeks and then at every scheduled follow-up visit. The primary endpoint is toxicity through day 30.

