8.2 Sample Size Calculation/Power Justification for the Primary Endpoint

This is a MTD determination study. Therefore, the power calculation is not relevant. A 3 to 6 subject per dose cohort with a total of 15 to 30 subjects is standard for a phase 1 trial (72).

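### One DLT among the first three men at the starting dose both stops the study (6.4.2.1) and expands the cohort to six (5.1.2.5, 6.3.2.4)

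*Combined protocol and SAP*

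**What the plan says.** Section 6.4.2.1, under the study stopping rules, reads in full "DLT in the first dose cohort". It gives no number of events, no qualifier and no cross-reference.

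Section 5.1.2.5 sets the dose-escalation rule. Its condition is "If one of three subjects experiences a dose-limiting toxicity (DLT", as defined in 6.3.2.3, and its action is "three additional subjects will be enrolled at that dose level". It continues: "If only one of six subjects experiences a DLT at a given dose level, the dose will escalate to the next cohort". Two DLTs at a dose mean that the MTD is exceeded, and then "additional subjects will be enrolled at the previous dose level if there were only three subjects at that dose".

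Section 6.3.2.4 repeats the expansion: "If 1 of 3 subjects in a cohort develops DLT, the cohort will be expanded to 6 subjects". It places the MTD below two DLTs in six, and it stops the trial only at two or more.

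Table 5 gives 3 to 6 subjects for every cohort, including the first. Section 3.1 plans "Fifteen to 30 men with locally recurrent prostate cancer after definitive radiotherapy", and section 8.2 justifies the size "with a total of 15 to 30 subjects is standard for a phase 1 trial".

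**The concern.** If exactly one of the first three men at 1 × 10^10 vp has a DLT, 6.4.2.1 ends the study without an MTD. Sections 5.1.2.5 and 6.3.2.4 require three more men at the same dose and allow escalation if none of them has a DLT. Whichever action is taken breaches a section of the protocol.

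This is the first dosing decision for a replication-competent vector carrying IL-12. It bears on subject safety and on the MTD, which is part of the primary objective (2.1). Nothing in the text decides it in advance, so as written it would be decided after the event has been seen.

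**Working it through.** **Where the rules agree and where they do not (first three subjects of cohort 1)**

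- 0 of 3 with a DLT: both allow escalation.
- 2 or 3 of 3: both stop, because the MTD is exceeded and there is no lower dose.
- Exactly 1 of 3: 6.4.2.1 stops; 5.1.2.5 and 6.3.2.4 expand to six.

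Table 5's range of 3 to 6 for cohort 1 does not resolve this. Cohort 1 can also reach six by de-escalation from cohort 2.

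**The plan's own figure.** Five cohorts of 3 to 6 give 5 × 3 = 15 and 5 × 6 = 30, which matches 3.1 and 8.2. If 6.4.2.1 governs, cohort 1 stays at three on the way up and the maximum is 3 + 4 × 6 = 27. That figure uses the trial stop in 6.3.2.4 after one de-escalation step. Repeated de-escalation under 5.1.2.5 alone could still reach 30.

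**Size of the conflict.** Let p be the true DLT rate at dose 1. The documents give no value, so the rates below are assumptions.

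- Conflicting outcome: P(1 of 3) = 3p(1−p)².
- Stop in cohort 1, literal 6.4.2.1: 1 − (1−p)³.
- Stop in cohort 1, expansion rule: P(≥2 of 3) + P(1 of 3) × [1 − (1−p)³].
- Escalation after 1 of 3 under the expansion rule: (1−p)³.

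At p = 0.10:

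- P(1 of 3) = 3 × 0.10 × 0.81 = 0.243.
- Literal stop = 1 − 0.729 = 0.271.
- P(≥2 of 3) = 0.028, so the stop under expansion = 0.028 + 0.243 × 0.271 = 0.0939.
- Check: 0.271 − 0.0939 = 0.1771 = 0.243 × 0.729.

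| Assumed p | Exactly 1 of 3 | Stop, literal 6.4.2.1 | Stop, expansion rule | Stopped by 6.4.2.1 but escalated by expansion rule |
|---|---|---|---|---|
| 2% | 5.8% | 5.9% | 0.5% | 5.4% |
| 5% | 13.5% | 14.3% | 2.7% | 11.6% |
| 10% | 24.3% | 27.1% | 9.4% | 17.7% |
| 15% | 32.5% | 38.6% | 18.6% | 20.0% |
| 20% | 38.4% | 48.8% | 29.1% | 19.7% |
| 30% | 44.1% | 65.7% | 50.6% | 15.1% |

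Once the conflicting outcome has occurred, 6.4.2.1 always stops. The expansion rule goes on to escalate in 85.7%, 72.9% and 61.4% of cases at p = 5%, 10% and 15%.

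**A second, smaller gap.** Suppose cohort 1 has 0 of 3, cohort 2 exceeds the MTD, and cohort 1 is then expanded. One DLT among the three added men gives 1 of 6. Section 6.3.2.4 makes dose 1 the MTD, while 6.4.2.1 read literally stops the study. The probability is (1−p)³ × P(cohort 2 exceeds the MTD) × 3p(1−p)². The middle term is the expansion-rule stopping formula at the dose-2 rate. With that rate equal to p or 2p:

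- p = 5%: 0.857 × 0.0266 × 0.135 = 0.3%, or 0.857 × 0.0939 × 0.135 = 1.1%.
- p = 10%: 0.729 × 0.0939 × 0.243 = 1.7%, or 0.729 × 0.2914 × 0.243 = 5.2%.
- p = 15%: 0.614 × 0.1862 × 0.325 = 3.7%, or 0.614 × 0.5057 × 0.325 = 10.1%.

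**The case against.** The best defence is that a specific rule overrides a general one. Section 6.4.2.1 concerns only the first cohort. It adds something to 6.3.2.4 only if it is stricter, so the authors may well have intended a first-dose safety stop. The defect would then be a missing cross-reference, and the literal reading errs towards protecting subjects.

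A second reading is that stopping means a halt for review. Section 6.4.2.2, next in the list, pairs stopping with re-evaluation of the injection procedure. Expansion could then follow a halt.

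Both readings are plausible, but neither is written down, and they lead to different actions. The first leaves no MTD, and the second may treat three more men. Section 6.4.2.1 has no re-evaluation or restart clause. Even if it does override the expansion rule, the de-escalation gap remains.

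Section 9.0 mentions a monitoring plan whose content is not reproduced. It might address the point, but that cannot be assumed, and the protocol sections would still disagree.

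The objection to the illustrated rates is fair. Trial 1 started at the same 1 × 10^10 vp and had no DLTs in 16 subjects (1.2.2.1), although its vector lacked IL-12. At true rates of 1% and 2% the conflicting outcome has probability only 2.9% and 5.8%. This lowers the chance that the problem arises but does not reconcile the rules. It is also true that the analysis is descriptive (8.3) and that no test is invalidated.

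**Conclusion.** The contradiction is present in the text and needs no outside figure to establish. On the way up it is confined to one outcome, exactly one DLT in the first three subjects at dose 1. There is a lesser gap if cohort 1 is expanded on de-escalation.

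Its likelihood depends on an unknown DLT rate: about 3% to 6% at assumed rates of 1% to 2%, and 13.5% to 32.5% at 5% to 15%. The calculations treat subjects as independent with a common rate at each dose.

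Because the outcome decides whether the trial continues and whether more men are treated at that dose, the text must be corrected before enrolment.

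**What to change.** The clinical team should choose one cohort-1 rule and make every section state it.

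- **Option A, standard expansion.** Reword 6.4.2.1 to *two or more DLTs in the first dose cohort (MTD exceeded per 6.3.2.4)*. The maximum stays at 30, and the de-escalation gap closes as well.
- **Option B, strict first-dose stop.** Keep 6.4.2.1. Add to 5.1.2.5 and 6.3.2.4 that expansion after 1 of 3 does not apply to the first three subjects of cohort 1. State that a later expansion of cohort 1 by de-escalation follows the 6.3.2.4 threshold of two or more DLTs. Restate the maximum in 3.1 and 8.2 as 27, and make clear that the 6.3.2.4 stop after one de-escalation step governs, since that figure depends on it.

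Table 5 keeps 3 to 6 for cohort 1 under both options. As a minor addition, 3.1 and 8.2 should say that 15 is the minimum only if all five cohorts open.

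The cost is a short text amendment: mainly one line for Option A, four sections for Option B. Neither adds patients or procedures.

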6.5 Measurement of Treatment Effect

Treatment effect will be based on post-treatment digital rectal examinations (DRE), PSA evaluations, bone and CT/MRI scans. DRE and PSA will be assessed at every scheduled follow-up visit. Bone and CT/MRI scans will be performed as clinically indicated.

6.6 Definition of Response Parameters

6.6.1 Freedom from Biochemical (PSA) Failure- The time to PSA failure will be measured from the date of the adenovirus injection to the date of a rise of \geq 2 ng/mL above the nadir PSA (71). Nadir PSA is defined as the lowest PSA value after the adenovirus injection and before the call date of PSA failure. The time of failure will be the date of the first PSA that is \geq 2 ng/mL above the post-treatment nadir.

6.6.2 Freedom from Clinical Failure- The time to clinical failure (local and/or regional/distant) will be measured from the date of the adenovirus injection to the date that clinical failure is first documented.

Local clinical failure is defined as having any ONE of the following:

6.6.2.1 Local progression, as measured by a \geq 25% increase in the product of the two largest perpendicular diameters of the prostate tumor at any time.

6.6.2.2 Failure of regression of palpable tumor by 2 years.

6.6.2.3 Redevelopment of a palpable abnormality after complete disappearance of previous abnormalities.

Note: In all above cases, unless clinically contraindicated, needle biopsy verification is required to document the presence of local tumor.

Regional/distant clinical failure is defined as having any ONE of the following:

6.6.2.4 Radiographic (CT or MRI) evidence of new or increased pelvic lymphadenopathy (measuring >1.5 cm on short axis) and/or histological confirmation of tumor.

6.6.2.5 The development of a new area of isotope uptake on bone scan relative to baseline that cannot be attributed to trauma and is clinically consistent with metastatic disease. Any questionable findings must be confirmed by other imaging modalities (e.g., MRI) and/or biopsy.

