3.2 Criteria for Subject Eligibility

To be eligible, the subject must have:

3.2.1 Biopsy-proven local recurrence of prostate cancer at least one year after the completion of definitive radiation therapy. The biopsy must be performed within 180 days of registration.

3.2.2 Evidence of biologically active disease as demonstrated by an unequivocally rising serum PSA level that is ≥ 2 ng/mL above the nadir.

3.2.3 PSA < 100 ng/mL.

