5.0 STUDY THERAPY AND PROTOCOL

5.1 Treatment Plan

5.1.1 Pretreatment Evaluations

5.1.1.1 History and physical examination including digital rectal exam (DRE).

5.1.1.2 Hematology- CBC/DP.

5.1.1.3 Blood chemistries- glucose, Na, K, Cl, Ca, Mg, P, CO₂, BUN, creatinine, AST/SGOT, ALT/SGPT, ALKP, bilirubin, serum protein, albumin, globulin, GFR, CPK, LDH, GGT, testosterone.

5.1.1.4 Diagnostic serum PSA.

5.1.1.5 Urinalysis, urine culture, and sensitivity.

- 5.1.1.6** Chest radiographs (PA and lateral).
- 5.1.1.7** Diagnostic imaging- bone scan and CT scan of the abdomen and pelvis within 90 days of registration.
- 5.1.1.8** Biopsy/pathology reviews- a TRUS-guided needle biopsy of the prostate (\geq 6 core) must be performed within 180 days of registration to confirm the presence of adenocarcinoma and to determine prostate volume. Biopsy cores should be kept separate, coded and submitted to Department of Pathology for analysis.
- 5.1.1.9** Molecular studies- presence of Ad5-yCD/*mutTK_{SR39}rep-hIL12* in blood by polymerase chain reaction (PCR). This is a baseline control for the post-treatment PCR assays and does not have to be completed before the subject can be enrolled.
- 5.1.1.10** Immunological studies- serum IL-12 and IFN- γ will be measured by enzyme-linked immunosorbent assay (ELISA). NK cell cytolytic activity will be measured by ^{51}Cr release or non-radioactive cytotoxicity assay. These are baseline controls for the post-treatment evaluations and do not have to be completed before the subject can be enrolled.
- 5.1.1.11** EPIC and EQ-5D instruments.
- 5.1.1.12** The subject will be required to meet with a urologic surgeon to discuss other treatments options such as salvage prostatectomy. This meeting must be documented in the patient's records.

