5.1.2.7 Intraprostatic Injection Procedure

Subjects will be seen as outpatients the day of the adenovirus injection. The injection procedure will be performed in a private treatment room with restricted access. Biosafety Level 2 procedures will be followed throughout.

Adenovirus injections will be performed transrectally under transrectal ultrasound guidance (TRUS) typically using 20 gauge needles. The subject will be placed in the left lateral decubitus position with the legs flexed and the knees brought up toward the chest. The buttocks are placed over the edge of the examining table to allow for the appropriate manipulation of the ultrasound probe. Prior to the adenovirus injection, the subject will receive a local injection of 1% lidocaine into the area surrounding the prostatic capsule. Two needle passes (one medial, one lateral) will be made in the left and right sides of the prostate starting at the base and proceeding toward the apex until all of the adenovirus is delivered.

Used syringes and needles will be disposed of properly. After the procedure, the treatment room will be cleaned with an approved disinfectant.

5.1.2.8 **Toxicity**

Injection procedure- Possible side effects of the injection procedure include infection, gross hematuria and urinary retention. Infection occurs in less than 1% of cases. Antibiotic therapy will be given as prophylaxis prior to and after the adenovirus injection. Gross hematuria following prostate biopsy occurs in less than 1% of cases and is usually self-limited. Injection of the adenovirus into the prostate may cause local swelling that could lead to acute urinary retention. A Foley catheter will be placed, if needed.

Ad5-*yCD/mutTK_{SR39}rep-hIL12* adenovirus- Based on the results of five phase 1/2 trials with similar oncolytic adenoviruses lacking IL-12 (36-44), likely adverse events attributable to the oncolytic adenovirus include transient flu-like symptoms (37 of 79 subjects or 47%) and transaminitis (32 of 79 subjects or 41%). The vast majority (> 94%) of these events were mild (grade 1) to moderate (grade 2). The flu-like symptoms typically resolve within a few days and can be alleviated with analgesics. The transaminitis is self-limiting and typically resolves within 2 weeks.

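### Section 6.6.2 has no local-failure criterion that clearly covers a first palpable abnormality in a man whose DRE was normal at entry, so such failures can be missed or dated late

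*Combined protocol and SAP*

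**What the plan says.** Section 2.2.2 makes freedom from biochemical/clinical failure (FFF) a secondary objective. Section 6.6.2 dates clinical failure from the adenovirus injection to first documentation. Local failure is any one of three findings:

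- Item 6.6.2.1 covers growth of 25% or more, described as an "increase in the product of the two largest perpendicular diameters of the prostate tumor at any time".
- Item 6.6.2.2 counts a tumour that can be felt and has not regressed once two years have passed.
- Item 6.6.2.3 deals with a finding that comes back on palpation, and is worded as "Redevelopment of a palpable abnormality after complete disappearance of previous abnormalities".

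A Note then applies to all three items, with an exception where biopsy is contraindicated on clinical grounds. It says that "needle biopsy verification is required to document the presence of local tumor".

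The eligibility criteria (section 3.2) ask for "Biopsy-proven local recurrence of prostate cancer at least one year after the completion of definitive radiation therapy" and an unequivocally rising PSA at least 2 ng/mL above nadir. Neither section 3.2 nor section 3.3 requires a palpable tumour.

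A DRE is required before treatment (5.1.1.1) and at each follow-up visit: 1, 3, 6, 9, 12, 18 and 24 months, then at least annually (6.2). Section 6.5 names DRE as a measure of treatment effect. The pretreatment TRUS biopsy is there to confirm adenocarcinoma and determine prostate volume (5.1.1.8). Follow-up bone and CT scans are prompted by bone pain or PSA failure (Table 7, 6.2.7, 6.2.8) or done as clinically indicated (6.5).

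**The concern.** A new nodule on DRE is a foreseeable sign of local progression in a man who entered on biopsy and PSA evidence alone, and the visit schedule is built to find it. The list of local-failure criteria, however, is written as if every man started with a palpable abnormality. If it is followed literally, staff who feel a first nodule have no clear category for it. They must leave it out, wait for another criterion, or improvise.

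At stake are the occurrence and date of clinical failure, which 6.6.2 defines as a response parameter of its own as well as a part of FFF. With so few subjects, each call visibly moves the reported proportion. A related question is how much the biopsy Note can do to confirm progression in men who all had a positive biopsy when they entered.

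**Working it through.** The plan states no figure for local failure, so there is nothing to reproduce. The main check sets the text against one case.

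**Step 1. The case.** An eligible man has a normal DRE at baseline. A first nodule is felt at a scheduled visit, say 9 months.

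| Criterion | What it presupposes | Does it cover him? |
|---|---|---|
| 6.6.2.3 | An earlier abnormality that disappeared completely | No; he had none |
| 6.6.2.2 | A palpable tumour not regressed by 2 years | Not at 9 months; on a loose reading at 24 months if the nodule persists, 15 months late (24 − 9) |
| 6.6.2.1 | A measured tumour and a reference product | Only if diameters were measured at baseline, which nothing schedules |

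On 6.6.2.1, the text does not name the reference (baseline or smallest value) or the method (DRE, TRUS, CT or MRI). If the baseline product is zero or unrecorded, a 25% increase is undefined.

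**Step 2. What the biopsy can show.** Positivity at entry is 100% by eligibility. The Note asks whether tumour is present, not whether it is new or has grown. The verifying biopsy would be a fresh one after treatment, since Table 7 schedules TRUS biopsy only before therapy.

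The only guide in the documents to later positivity is Trial 1 (section 1.2.2.1.2), where 2 of 16 enrolled subjects were negative at 1 year. The number biopsied is not given. Assuming all 16 were:

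- still positive: 14/16 = 87.5%, exact (Clopper-Pearson) 95% CI 61.7% to 98.4%.

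If fewer were biopsied, the positive share is lower. The check is weak as a filter, but not automatic.

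**Step 3. How sensitive the 25% rule is.** With equal growth in both diameters, √1.25 = 1.118, or 11.8% per diameter.

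Suppose there is no true growth, and log-normal measurement error with coefficient of variation c per diameter (an assumption; the documents give none). The log ratio of two products has SD 2√ln(1 + c²), and the rule is crossed when it exceeds ln 1.25 = 0.223.

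| Assumed c | SD | 0.223/SD | Crossed at one visit |
|---|---|---|---|
| 5% | 0.100 | 2.23 | 1.3% |
| 10% | 0.200 | 1.12 | 13.2% |
| 15% | 0.298 | 0.75 | 22.7% |

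This shows why the reference and method need to be fixed. It does not estimate false calls in this trial, because the protocol does not schedule diameter measurements.

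**The case against.** **The criteria may still catch the case.** 6.6.2.1 refers to the prostate tumour, not a palpable one, and TRUS and CT are done before treatment. 6.6.2.2 does not say that the tumour had to be palpable at entry. A new nodule that persists to 2 years could qualify under 6.6.2.2, and one that later grows 25% might be argued to qualify under 6.6.2.1. This stands in part: it rules out saying that a first nodule can never be recorded. It leaves ambiguity, delay and reliance on a measurement that the plan does not request.

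**PSA failure will often come first.** Every man enters with a rising PSA, and a rise of 2 ng/mL above nadir ends FFF. With Trial 1's mean post-treatment doubling time of 31 months (Table 2) and assumed nadirs of 2, 5 and 10 ng/mL, the time is 31 × log₂((nadir + 2)/nadir), or about 31, 15 and 8 months. This stands for the composite. It does not repair the clinical-failure time, which has its own date.

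**A reader might infer that local failure is misclassified in both directions.** The documents do not support that:

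- The biopsy is an added condition. It can remove failure calls but never create one.
- A positive biopsy at entry does not satisfy the Note, which calls for a new biopsy; two Trial 1 subjects became negative.
- A nodule that has not regressed at 2 years is a failure by the protocol's own definition, not an error.
- Section 5.1.2.8 says only that "Injection of the adenovirus into the prostate may cause local swelling"; the first scheduled follow-up DRE is at 1 month.

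**Stricter repairs could do harm.** Dropping the biopsy and using the smallest product as reference from month 3 would raise false calls. In a simulation with no true growth, measurement at all 7 visits to 24 months, and per-diameter error of 5%, 10% or 15% (all assumed), a baseline reference with a biopsy passed by 87.5% gives false calls in about 6%, 37% and 52% of men. The stricter rule without biopsy gives about 21%, 84% and 96%. A month-3 start would also discard early progression. This objection stands, and the fix below avoids those changes.

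**Conclusion.** The gap is real and follows from the text alone: no local-failure criterion clearly covers a first palpable abnormality in a man with a normal DRE at entry, so his local failure can be missed or dated late. A positive verifying biopsy shows that tumour is present but cannot by itself separate persistent from progressing tumour. Its protection against over-calling is therefore limited, though not zero.

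The consequence is modest. Local failure is one component of a secondary endpoint that also counts PSA failure. Section 8.1.2 gives FFF no hypothesis, section 8.3 makes the analysis descriptive, and 15 to 30 men are planned. The primary toxicity and MTD objective is unaffected. The number of men exposed to the gap cannot be computed, because the documents give neither the share with a normal DRE at entry nor a rate of first nodules. The conclusion rests on reading the three criteria as a closed list, as 6.6.2 presents them. The biopsy and measurement-error figures are illustrative and depend on the assumptions stated with them.

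**What to change.** 1. Add a local-failure criterion to 6.6.2: *new palpable abnormality on DRE in a subject with none at baseline*. Keep the existing biopsy Note and apply it to this criterion too.
2. Record baseline palpability and, where measurable, the two tumour diameters at the pretreatment DRE or imaging that is already required. In 6.6.2.1, name that baseline value, obtained by the same method, as the reference for the 25% increase.
3. State in the reporting plan that a positive verifying biopsy documents the presence of tumour, not its progression.

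Leave 6.6.2.2 as it is.

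The cost is protocol wording and a few form fields, with no new scheduled visits or procedures. A first nodule would now fall under the existing biopsy Note. Freedom from clinical failure may look slightly less favourable, because first nodules would be counted when they are found.
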